	
Any patient receiving rescue medication or parenteral hydration will be deemed a treatment failure.
 
Metoclopramide 0.3 mg/kg, maximum dose 10 mg, administered intravenously will be the default rescue medication. Oral metoclopramide or other antiemetics administered either intravenously or orally may be used at the investigator's discretion. However, patients are not to receive ondansetron or other 5-HT3 antagonists by any route for at least 24 hours after administration of study medication. The following 5-HT3 antagonists are available in the US: alosetron (Lotronex), dolasetron (Anzemet), granisetron (Sancuso and others), ondansetron (Zofran, Zuplenz and others), palonsetron (Aloxi).
 
Oral fluids will be administered as tolerated once a patient has not vomited for 30 minutes after dosing with study medication (second dose for those patients receiving 2 doses in the ED). Guidelines for administration of oral fluids are shown on page 20, section 4.4.1, of the protocol.
 
Patients tolerating oral fluids will be discharged once deemed stable by the attending physician but not prior to 4 hours after dosing. On discharge, patients will be given 3 additional doses of study medication to take once daily if necessary.
 
Patients who do not tolerate oral fluids may receive parenteral hydration. Data will be collected daily for up to 4 days following study initiation (until symptoms have resolved) to ascertain whether the patient had further vomiting, other sequelae of the acute gastroenteritis or required further medical care for the gastroenteritis. Data may be collected by entry by the patient or a caregiver into a web-based system or on paper, or by telephone contact daily from a study staff member. If during the follow-up period, symptoms progress or worsen or new symptoms develop, the patient may be asked to return for further evaluation. If by day 4 after discharge (i.e., the day after the last dose of study medication), the patient still notes gastroenteritis symptoms, he or she will be instructed to return for further evaluation.

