cPrior to discharge, patients will be given diary pages to record their course after discharge. Patients will be contacted each day following treatment to a maximum of 4 days to determine whether they had further nausea and vomiting after leaving the emergency department, the occurrence and quality of bowel movements, including assessment using the Bristol stool scale (Appendix I), and the nature, occurrence and severity of other symptoms, whether they required further care for the acute gastroenteritis, and details regarding the continuation, if any, of the illness. If symptoms persist for 3 or more days after study entry, the patient is to be instructed to return for further evaluation.

dTo include all medications taken within 7 days prior to study entry, all treatments (including parenteral fluids) on the day of study entry, and all medication, including rescue medications, from the time of study entry through last follow-up.

ePatients are to receive the first dose of study medication within one hour of signing informed consent.

fPatients may take study medication daily for up to 3 days after study entry (maximum total of 4 doses, plus one additional if patient vomits within 15 minutes of first dose) if symptoms persist. Patients should stop taking study medication if symptoms have resolved, though they may resume study medication once daily if symptoms recur after discontinuation. Patients are not to take any remaining study medication after day 4. They will be given mailers to return any unused study medication.

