## 4. Study Design

### 4.1 Overview

Patients presenting to the emergency department who fulfill entry criteria will be asked to participate. A screening log will be kept listing all patients considered with reasons for patients not entering the study. Any patient whose information is reviewed in consideration for the study, even if not actually approached, is to be included in the screening log. The screening log will differentiate between those who are prescreened, i.e., who are reviewed but never progress to request for consent, from those who are screened, i.e., who are approached for consent, whether or not they actually sign consent or eventually participate in the study. Qualifying patients, once they have signed consent, will be stratified by age ( $\geq$  vs <age 18) and randomized 60:40 to RHB-102 or matching placebo. All patients will undergo laboratory testing and ECG, as specified below, once they have signed consent. However, only results of the pregnancy test (for women of childbearing potential) and a finger stick blood glucose (for patients with type 2 diabetes mellitus controlled by diet or oral medications) are required prior to treatment.

Patients will be started on oral fluids  $\geq$ 30 minutes after taking study medication (second dose for patients who receive 2 doses in ED) if they have not vomited during that period. Intravenous hydration should not be administered unless the patient has vomited or is clearly unable, after a reasonable period of time has elapsed since administration of study medication, to tolerate oral fluids.

At  $4\pm0.25$  hours after initial dosing, all patients are to have a repeat 12-lead ECG. Once stable, but not less than 4 hours after initial dosing, patients may be discharged from the emergency department. If a patient leaves the ED less than 4 hours after dosing, an ECG should be obtained if at all possible, even if the patient is leaving against protocol requirements.

On discharge, patients will be given an additional 3 doses of study medication to take at 24-hour intervals if nausea persists. Patients will be contacted daily for 4 days after discharge to determine their condition. Those patients who have persistent, worsening or recurrent nausea and/or vomiting during the follow-up period may be asked to come in for follow-up assessment by study personnel.

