#### 4.5 Duration of Treatment

On discharge, patients who have not had further vomiting and have not required rescue medication in the emergency department will be given 3 additional doses of study medication to take once daily if necessary. Patients will be instructed to take additional study medication if they are nauseated (whether persistent or recurrent) or have any vomiting. However, patients are not to take study medication more than 3 days after study entry. Thus, if a patient receives an initial dose of study medication in the emergency department, feels well the next day and does not take study medication, but subsequently has a recurrence of symptoms, that patient may not take the remaining dose of study medication on day 5. Rather, the patient should return for reassessment during the follow-up period.

Patients or their caregivers are to complete a diary each day for 4 days, recording episodes of vomiting, diarrhea, presence and severity of nausea, presence/development of other signs or symptoms related to the gastroenteritis, and occurrence of adverse events. This diary may be completed either on paper or through a web-based system. Alternatively, patients or their caregivers will be contacted daily for up to 4 days following study initiation (until symptoms have resolved) to ascertain whether the patient had further vomiting, other sequelae of the acute gastroenteritis or required further medical care for the gastroenteritis. If symptoms persist for 3 days after study entry, the patient will be instructed to return for further evaluation on the third or fourth day.

For patients discharged prior to 8:00 pm, the ED day diary page is to be completed. The ED day diary page is to include only information regarding events after discharge from the ED; information on events during the patient's ED stay is not to be repeated in the diary. For those discharged 8:00 pm to midnight, or later, diary information is to be recorded only on the follow-up diaries. But vomiting episodes and adverse events occurring between 8:00 pm and midnight the preceding day should be included in the information captured.

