#### 4.6 Discontinuation of Treatment

Patients may take study medication daily for up to 4 days (day 1 medication is the one or two tablets administered in the emergency department).

- If a patient vomits or otherwise receives rescue medication in the emergency department, he or she is not to receive additional study medication, even if nausea and/or vomiting is controlled with rescue medication.
- If the QTc interval at 4 hours after initial dose of study medication is >500 msec, study medication is to be discontinued.
- Patients experiencing recurrent nausea or vomiting after discharge from the emergency department and initial discontinuation of study medication due to resolution of symptoms may opt to resume study medication.

If a patient experiences an adverse event, regardless of relationship to study medication, which, in the investigator's opinion endangers or makes it difficult to evaluate the patient, the investigator may elect to have the patient stop study medication.

If once on study, a patient requires a medication which may prolong the QTc interval, he or she should not receive further study medication. However, evaluation of the patient should continue per protocol.

Patients may elect to discontinue treatment at any time.

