Patients will be contacted at least once daily for 4 days after discharge from the emergency department to question them about the presence of gastroenteritis symptoms and adverse events, to ask if and when they took study medication, and to ask whether they have returned to normal daily activities. The information recorded by the patient on his/her diary card will form the basis for data collected in the follow-up calls. If during the follow-up period, symptoms progress or worsen or new symptoms develop, the patient may be asked to return for further evaluation. If by day four after discharge (i.e., the day after the last dose of study medication), the patient still notes gastroenteritis symptoms, he or she will be instructed to return to see the investigator or his/her designate for further assessment. In addition, if the investigator is concerned that a patient may not be entering the data promptly and appropriately or as an added stimulus to data entry by the patient, the investigator may also contact the patient.

For patients returning due to persistent gastroenteritis 3 days after discharge from the ED, an interim history and physical examination will be performed. Laboratory studies may be performed if clinically indicated, and results of these studies will be entered into the CRF.

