7. ENDPOINTS AND COVARIATES

7.1. Efficacy Endpoint(s)

- 1) Primary Efficacy Endpoint: the proportion of patients who fulfill all the following 3 criteria from 30 minutes after first administration of study medication until 24 hours after the first dose of study medication:
 - a. absence of vomiting
 - b. no use of rescue medication, and
 - c. no intravenous hydration

If all of the above three criteria are fulfilled, the patient is considered a treatment success for the primary analysis. If one or more of the above three criteria are not fulfilled, i.e., the patient either experiences vomiting, receives rescue medication or receives intravenous hydration from 30 minutes through 24 hours after the first dose of study medication, the patient is considered a treatment failure.

Based on the 2nd blinded dry run conducted on [REDACTED], there were 28 subjects who did not have all the information needed to determine per the algorithm used if they met the primary endpoint successfully. For 17 patients, all treated under amendment 1 or 2, in which the primary endpoint was treatment success on emergency department discharge, the reason for not having complete information was the lack of an ER day diary. For these patients, based on all follow up data available, no treatment failure events occurred. Therefore, these patients are considered treatment successes. Among the other eleven, data were reviewed and several queries issued. Based on this review, patients were assessed by the medical monitor to be treatment successes (n=4), failures (n=1) or unknown (n=6). The adjudicated primary endpoint outcomes will be used for the primary analyses.

2) Secondary and Tertiary Efficacy Endpoints:

- Treatment success, as defined above, through 4 days following first dose of study medication
- Proportion of patients who experience or require each of the components of treatment failure:
 - Vomiting
 - Rescue antiemetic therapy
 - Intravenous hydration
- Severity of nausea
- Incidence and severity of diarrhea
- Incidence and severity of other symptoms of gastroenteritis
- Time from first dose of study medication to discharge from ED, extended observation unit or hospital, whichever comes last
- Days to resumption of normal activities (work/school/household)
- Proportion of patients requiring hospitalization
- Proportion of patients returning to emergency department for gastrointestinal symptoms within 4 days of initial discharge

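### The protocol gives two rules for how long patients are followed; the one that stops at symptom resolution can misclassify treatment success through 4 days

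*Protocol*

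**What the plan says.** Two places end follow-up when the patient is well. The synopsis, under Methodology, says "Data will be collected daily for up to 4 days following study initiation (until symptoms have resolved"), and applies this to web, paper and telephone collection alike. Section 4.5 attaches the same limit to daily contact, which it offers as the alternative to the diary: patients or caregivers are "contacted daily for up to 4 days following study initiation (until symptoms have resolved").

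Other places set no such limit. Section 4.1 says "Patients will be contacted daily for 4 days after discharge to determine their condition", and SAP 3.1 repeats this. Section 5.2.3 says "Patients will be contacted at least once daily for 4 days after discharge from the emergency department". In the same paragraph as its stopping wording, 4.5 says "Patients or their caregivers are to complete a diary each day for 4 days". Note c to the assessment schedule says "Patients will be contacted each day following treatment to a maximum of 4 days", which sets a ceiling without saying what may shorten it.

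The protocol also provides for relapse. Section 4.6 lets "Patients experiencing recurrent nausea or vomiting after discharge from the emergency department and initial discontinuation of study medication due to resolution of symptoms" resume study drug, and 4.5 describes a patient who is well the next day and then has symptoms again.

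The endpoint that depends on this follow-up is listed in SAP 7.1: "Treatment success, as defined above, through 4 days following first dose of study medication". SAP 6.2.2 calls it the first secondary endpoint.

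**The concern.** If contact may end once a patient feels well, the length of observation depends on the outcome being measured. A patient who resolves on day 2 and vomits on day 3 is recorded if the site follows 5.2.3. If the site follows the synopsis, or the contact route in 4.5, the event may never be recorded. Both sites would be compliant.

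What is at stake is whether success through 4 days means that no failure event occurred, or only that none was seen while someone was still asking. The SAP does not settle this. Sections 8 and 9.2 impute dropouts and unknown outcomes as failures for the primary analysis. Section 9.3 carries the statistical test over to other proportion endpoints but names no imputation rule for them. A patient whose contact ended as the synopsis allows is not clearly a dropout.

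**Working it through.** The plan states no figure on this point, and the sample size does not depend on it. For orientation, 40% against 20% failure at two-sided 0.01, 90% power and 60:40 allocation gives 127 + 191 = 318 (pooled variance, no continuity correction), against the stated 320.

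**Step 1: the texts side by side.**

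| Place | Duration | Stops at resolution? |
|---|---|---|
| Synopsis, Methodology | up to 4 days | yes, all data collection |
| Protocol 4.5, contact route | up to 4 days | yes |
| Protocol 4.5, diary | each day for 4 days | no |
| Protocol 4.1; SAP 3.1 | daily for 4 days | no |
| Protocol 5.2.3 | at least daily for 4 days | no |
| Schedule note c | each day, maximum 4 days | not stated |

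These cannot all be followed for a patient who resolves before day 4. Patients who fail within 24 hours are a separate case: 5.2.3 gives them a single call 72-96 hours after discharge, and they already count as failures through 4 days.

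**Step 2: what a missed relapse does.** The documents give neither a relapse rate nor the share of patients whose contact ended early, so the following is illustration only. Let

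- S = 24-hour success, 80% on RHB-102 and 60% on placebo (from the design failure rates of 20% and 40% in protocol 7.1);
- r = share of those successes with a failure event between 24 hours and day 4 (assumed 5-20%);
- u = share of those successes whose contact ended early with no other record, taken as unrelated to relapse (assumed 50-90% on RHB-102, 50% on placebo).

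Then

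- true 4-day success = S(1 - r);
- silence read as success = S(1 - r) + S·u·r;
- silence imputed as failure = S(1 - u)(1 - r).

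With r = 10% and u = 70% / 50%:

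- true: 0.80 × 0.90 - 0.60 × 0.90 = 72.0 - 54.0 = 18.0 points;
- silence as success: (72.0 + 5.6) - (54.0 + 3.0) = 20.6 points;
- silence as failure: 0.80 × 0.30 × 0.90 - 0.60 × 0.50 × 0.90 = 21.6 - 27.0 = -5.4 points.

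| r | u, RHB-102 / placebo | True difference | Silence = success | Silence = failure |
|---|---|---|---|---|
| 5% | 50% / 50% | 19.0 | 19.5 | 9.5 |
| 10% | 50% / 50% | 18.0 | 19.0 | 9.0 |
| 10% | 70% / 50% | 18.0 | 20.6 | -5.4 |
| 20% | 90% / 50% | 16.0 | 24.4 | -17.6 |

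Over the assumed ranges, reading silence as success adds S·u·r: 2.0 to 14.4 points on RHB-102, 1.5 to 6.0 on placebo, and 0.5 to 8.4 to the difference.

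**Step 3: is the direction fixed?** No. If S, u and r are equal in the two arms, S·u·r is equal and the difference is unbiased when silence is read as success. If contact stops more often on placebo (u = 50% / 70%, r = 10%), the additions are 0.80 × 0.50 × 0.10 = 4.0 and 0.60 × 0.70 × 0.10 = 4.2 points, and the difference falls by 0.2. Imputing failure lowers success in both arms.

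**The case against.** The strongest reply is that the stopping wording is the minority text. Sections 4.1 and 5.2.3 and SAP 3.1 already require 4 full days. Patients who succeed in the ED leave with a diary card, and 5.2.3 makes that card the basis of the follow-up calls, so a relapse after the last call could still be on paper. A recurrence in the sense of 4.6 may also be nausea alone, which is not a treatment failure. All of this stands, and it is why the finding is a contradiction to reconcile and not a settled rule that contact stops. It does not remove the problem, because the synopsis limit covers diary data too and 4.5 presents contact as an alternative to the diary.

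A reader might infer that relapses are missed mostly on RHB-102, because it resolves symptoms sooner, and that its 4-day success is therefore overstated. The documents do not support that. They give no resolution rate by arm. The 80% and 60% are design assumptions about freedom from vomiting, rescue and intravenous hydration, not about symptoms having resolved. The sign also depends on an imputation choice that the SAP does not make.

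A reader might also infer that the primary endpoint is exposed, since a patient discharged at 4 hours has 24 - 4 = 20 hours still to run. This is weak. Section 4.5 requires an ED day diary page for discharges before 8:00 pm and captures later evening events on the follow-up pages. Unknown outcomes are imputed as failures, and SAP 9.2 adds all-responder and worst-case analyses. The 17 patients whom SAP 7.1 counts as successes without that page were treated under amendment 1 or 2, when the endpoint was assessed at ED discharge; the stated reason is the missing page, not contact that ended at resolution. Those cases do show that an absence of recorded events has been read as success, which is a reason to write the 4-day rule down.

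**Conclusion.** The contradiction is plain on the face of the documents. Because relapse is foreseen and success is scored through 4 days, a compliant site can miss failure events, and the SAP does not say how the affected patients are classified. Success through 4 days may therefore be misclassified.

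The size is unknown. The figures above rest wholly on assumed relapse and stopping rates and show only that the result can turn on the unwritten choice. Silence read as success overstates success in an arm; imputation as failure understates it. Neither direction can be claimed for the comparison between arms.

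The 24-hour primary endpoint is largely protected. An effect there would need resolution, end of contact and relapse all before 24 hours, with no diary entry. Even then, inflation of the difference needs unequal loss. If 10% of failures were missed in both arms (an assumption), the difference would shrink from 20 to 0.36 - 0.18 = 18 points; only if they were missed on RHB-102 alone would it grow, to 0.40 - 0.18 = 22.

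**What to change.** In the protocol, delete the parenthesis about symptom resolution from the synopsis and from 4.5. State that patients who have not failed within 24 hours have diary or contact data through day 4 whether or not symptoms have resolved, as 4.1, 5.2.3 and SAP 3.1 already require. The single 72-96 hour call that 5.2.3 sets for patients who fail within 24 hours stays as it is.

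In the SAP:

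- state how success through 4 days is classified when contact ended early;
- report the number of such patients by arm;
- analyse 4-day success with these patients imputed as successes and again as failures.

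The cost is a wording change, a short SAP rule, one table and two further runs of the age-stratified CMH test. No calls are added beyond those already required. The supplemental SAP records unblinding on June 3, 2017, so the wording change cannot recover data for patients already followed, and a classification rule added after that date should be labelled post hoc.

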#### 4.6 Discontinuation of Treatment

Patients may take study medication daily for up to 4 days (day 1 medication is the one or two tablets administered in the emergency department).

- If a patient vomits or otherwise receives rescue medication in the emergency department, he or she is not to receive additional study medication, even if nausea and/or vomiting is controlled with rescue medication.
- If the QTc interval at 4 hours after initial dose of study medication is >500 msec, study medication is to be discontinued.
- Patients experiencing recurrent nausea or vomiting after discharge from the emergency department and initial discontinuation of study medication due to resolution of symptoms may opt to resume study medication.

If a patient experiences an adverse event, regardless of relationship to study medication, which, in the investigator's opinion endangers or makes it difficult to evaluate the patient, the investigator may elect to have the patient stop study medication.

If once on study, a patient requires a medication which may prolong the QTc interval, he or she should not receive further study medication. However, evaluation of the patient should continue per protocol.

Patients may elect to discontinue treatment at any time.

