### Notes:

aHistory, physical including VS (pulse, respiratory rate, blood pressure, temperature and, at baseline only height and weight), informed consent. For all patients: CBC with platelet count, biochemical profile and ECG. Urinalysis is required for all patients  $\geq$  age 40 and with a history of diabetes; it is optional for other patients. Blood and urine specimens should be taken expeditiously at the beginning of assessment, but patient entry into the study and treatment need not wait for lab results (other than pregnancy test and fingerstick blood glucose when required) unless clinically indicated. After phlebotomy, a saline lock may be placed so that the patient will not require an additional needle stick should he/she require intravenous fluids subsequently. History of present illness should include questioning regarding precipitating/causative factors, as well as recording of number and character of emetic and diarrheal episodes.

Patients with diet-controlled type 2 diabetes mellitus are to have a finger stick blood glucose.

For women of childbearing potential, as defined in the exclusion criteria: urine or serum pregnancy test. Negative pregnancy test result must be obtained prior to treating a patient on study.

bPatients are to be observed in the emergency department for a minimum of 4 hours after initial dose of study medication, with VS at least once every hour and recording of intake (both oral and parenteral) and number of voidings. All episodes of vomiting and diarrhea are to be recorded, and severity of nausea at baseline and every hour while in the ED noted.

All patients are to have a repeat ECG 4±0.25 hours after initial dosing with study medication. At a minimum of 4 hours after initial administration of study medication, after repeat ECG, patients may be discharged when clinically appropriate. **Any patient who has an on-study ECG showing QTc>500 msec must have a follow-up ECG showing resolution of the QTc prolongation. Timing of follow-up ECG(s) at investigator discretion. If the QTc does not decrease below 500 msec during follow-up, the medical monitor must be contacted to discuss further follow-up.**

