#### 5.2.3 Procedures after discharge from emergency department:

Any patient who has a post-dosing ECG showing QTc>500 msec must have a follow-up ECG within 72 hours of initial dosing showing resolution of the QTc prolongation. This may be performed on an inpatient or outpatient basis at the investigator's discretion. If the QTc does not decrease below 500 msec during initial follow-up, the medical monitor must be contacted to discuss further follow-up.

If a patient vomits from 30 minutes after taking the first dose of study medication until 24 hours after the first dose of study medication or requires rescue antiemetic or parenteral hydration during that period, even without vomiting, he or she will be considered a treatment failure. In that case, the only post-emergency department follow-up will be a call 72-96 hours after discharge from the emergency department to ascertain whether the patient's symptoms have

resolved, whether any adverse events occurred, and whether the patient required further medical follow-up, either in an emergency department or other medical facility.

Prior to discharge, patients who are treatment successes (i.e., no vomiting, no rescue medication and no parenteral hydration while in emergency department) will be given a diary card to record:

- all episodes of vomiting and bowel movements, with description of each bowel movement
- severity of nausea (on a 5-point Likert scale) three times a day: before breakfast or the time at which the patient usually eats breakfast, between 1:00-2:00 pm, and at bedtime
- any symptoms the patient may have related to gastroenteritis, such as chills, fever, abdominal pain
- adverse events
- medications taken, either for gastroenteritis (study medication and others) or other conditions

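### The mandatory QTc >500 msec stop in Protocol 4.6 names only the 4-hour ECG; the same value on another post-dose ECG requires follow-up but leaves stopping to discretion

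*Protocol*

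**What the plan says.** Three places in the protocol act on a QTc above 500 msec.

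- Section 4.6 contains the only mandatory stop: "If the QTc interval at 4 hours after initial dose of study medication is >500 msec, study medication is to be discontinued".
- Note b to the assessment schedule sets a follow-up duty: "Any patient who has an on-study ECG showing QTc>500 msec must have a follow-up ECG showing resolution of the QTc prolongation". It adds: "Timing of follow-up ECG(s) at investigator discretion".
- Section 5.2.3 repeats the duty with a deadline: "Any patient who has a post-dosing ECG showing QTc>500 msec must have a follow-up ECG within 72 hours of initial dosing".

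Note b and 5.2.3 both require contact with the medical monitor if the QTc does not come down. Neither says that study drug stops.

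The ECG scheduled for everyone is at 4±0.25 hours. The protocol also provides for others. Section 4.1 says: "If a patient leaves the ED less than 4 hours after dosing, an ECG should be obtained if at all possible", and section 5.2.2 asks for the same tracing just before such a patient goes. Section 6.6 covers ECGs that the protocol does not require.

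On home dosing, section 4.1 provides "an additional 3 doses of study medication to take at 24-hour intervals if nausea persists". Section 4.5 gives these tablets to patients who have neither vomited further nor needed rescue in the emergency department. Section 8 gives them to patients who have not failed before discharge. Neither section mentions QTc.

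**The concern.** The follow-up duty has a wider trigger than the stop. A patient with a QTc above 500 msec on an ECG other than the 4-hour one must have a repeat ECG, but no rule says that dosing must stop until the repeat shows resolution. If that patient has not failed treatment, the dispensing rules still send three tablets home, to be taken for nausea or vomiting.

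The protocol is stricter in neighbouring situations. A screening QTc above 450 msec bars entry (3.2). A patient who comes to need a QT-prolonging medicine gets no more study drug (4.4, 4.6). A measured QTc above 500 msec seems to deserve no weaker rule merely because it was recorded at another time. What is at stake is the safety of a few individual patients; the efficacy result is not involved.

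**Working it through.** The plan gives no figure on this point to reproduce. The check is a comparison of the rules, followed by a short dose count.

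**Step 1. Rule by type of ECG, for a QTc above 500 msec**

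| ECG | Follow-up ECG | Study drug |
|---|---|---|
| Scheduled, 4±0.25 h | Required (note b, 5.2.3) | Mandatory stop (4.6) |
| Early leaver, before the 4-hour ECG (4.1, 5.2.2) | Required | No mandatory stop, unless read as the 4-hour ECG taken early |
| Unscheduled, after dosing (6.6) | Required | No mandatory stop |

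**Step 2. Other routes to a stop.** The remaining provisions are vomiting or rescue in the emergency department, need for a QT-prolonging medicine, serotonin syndrome, and the adverse-event clause of 4.6. Only the last can be reached by a QTc value alone. Section 6.6 sends clinically significant ECG changes to the adverse-event page. Section 4.6 then lets the investigator stop drug if, in the investigator's opinion, the event endangers the patient or hinders evaluation. That is a permission and not a requirement. The SAP has no stopping rule.

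**Step 3. Who could still take drug.** The patient must have an ECG outside the 4-hour slot, with QTc above 500 msec, and must not have vomited or needed rescue in the emergency department. Admitted patients continue drug only at the investigator's discretion (4.2), so they add little.

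**Step 4. Home doses before the follow-up ECG**

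Inputs:
- Three home tablets at 24-hour intervals (4.1), counted here from the first dose, so due at 24, 48 and 72 h.
- Follow-up ECG at time t, no later than 72 h after the first dose (5.2.3).
- 24 mg of ondansetron per RHB-102 tablet (8).

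Formula: doses before follow-up = number of k in {1, 2, 3} with 24 × k < t.

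- t = 24 h: 0 doses.
- t = 48 h: 1 dose, 24 mg.
- t = 72 h: 2 doses, 2 × 24 = 48 mg.

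The third dose falls due at the 72-hour limit itself. Two doses is a ceiling: home doses are taken only for symptoms, and 128 of the 320 planned patients (40%) receive placebo.

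**The case against.** The strongest reply is that the early-leaver ECG is simply the 4-hour ECG brought forward. Section 5.2.2 puts both in one bullet, which supports that reading. But 4.6 does not adopt it, and it does not reach unscheduled ECGs.

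The second reply is that the standard route is fully covered. Discharge is permitted only after 4 hours and the repeat ECG, so an early leaver has already departed from the protocol. This stands and limits the weight of the point. Still, the protocol asks for an ECG in exactly these patients, and SAP 6.5 lists the failure to stay as a significant deviation, so the case was foreseen.

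The third reply is that other safeguards remain: the discretionary stop, the mandatory follow-up ECG and the medical monitor. This also stands. An investigator who sees such a value would probably stop drug.

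A reader might be tempted by four stronger inferences that the documents do not support.

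- *Three home doses (72 mg) could precede the repeat ECG.* Note f says "Patients may take study medication daily for up to 3 days after study entry". If that means calendar days, a first dose at 14:00 with home doses at 08:00 gives 18, 42 and 66 h. But 4.1 and SAP 3.1 specify 24-hour intervals. Nor does note b's freedom over timing remove the 72-hour limit in 5.2.3.
- *About 27 patients are exposed to the gap.* SAP 6.2.2 gives major deviations in 42% of the 7% of patients at small sites and in 6% of the others: 0.07 × 0.42 + 0.93 × 0.06 = 0.0852, and 0.0852 × 320 = 27.3. This counts major deviations of every kind. It bounds early leavers only if leaving early is classed as major, and it ignores that ECGs were required of all patients only from amendment 4 (SAP 9.1). Going on to affected patients would also need a rate of QTc above 500 msec, which the documents do not give.
- *Patients could not be told in time.* Section 5.2.3 does say "the only post-emergency department follow-up will be a call 72-96 hours after discharge from the emergency department", but that concerns treatment failures. Others are contacted at least daily, and arranging the required follow-up ECG already means contact. No section describes an ECG read only after the patient has gone home.
- *No stop is available.* One is available; it is discretionary.

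**Conclusion.** The mismatch holds on the literal text: one threshold, with a narrower trigger for stopping than for follow-up. For early-leaver ECGs (unless read as the 4-hour ECG) and unscheduled post-dose ECGs, stopping is discretionary and home dispensing carries no QTc condition.

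Very few patients are likely to be affected; the number of such ECGs and the rate of QTc above 500 msec on them are both unknown. For an affected patient, the ceiling of two home doses rests on 24-hour spacing from the first dose and on the 72-hour follow-up limit being kept. Severity is minor. Sample size, primary endpoint and primary analysis are unaffected.

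**What to change.** In 4.6, change the trigger of the mandatory stop from the 4-hour reading to a QTc above 500 msec on any ECG taken after dosing. This also settles whether the early-leaver ECG counts. In 4.5 and section 8, state that home tablets are given subject to 4.6.

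The cost is one reworded sentence and two cross-references. No new ECG, visit or analysis is needed. The downside is that a few patients go without home doses.
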